## **3.2 Exclusion Criteria**

3.2.1 Patients who have received more than two prior therapies.

3.2.2 Concurrent use of valproic acid is not allowed.

3.2.3 Patients may not be receiving any other investigational agents.

3.2.4 Patients with untreated CNS metastases. Patients should have a head CT/MRI within 28 days prior to treatment initiation. Patients with previously excised/gamma knifed solitary or oligometastases and controlled disease are eligible.

3.2.5 Any medical condition that would preclude adequate evaluation of the safety and toxicity of the study combination.

3.2.6 Uncontrolled intercurrent illness including, but not limited to, ongoing or active infection, symptomatic congestive heart failure (New York Association Class II, III, or IV), angina pectoris requiring nitrate therapy, recent myocardial infarction (< the last 6 months), cardiac arrhythmia, history of CVA within 6 months, hypertension (defined as blood pressure of >160 mmHg systolic and/or >90 mmHg diastolic on medication) history of peripheral vascular disease, or psychiatric illness/social situations that would limit compliance with study requirements.

3.2.7 Patients with a history of allergy to entinostat or other medications that have a benzamide structure (i.e. tiapride, remoxipride, and clebopride).

3.2.8 Pregnant women are excluded from this study because entinostat is a HDAC inhibitor agent with the potential for teratogenic or abortifacient effects. Because there is an unknown but potential risk for adverse events in nursing infants secondary to treatment of the mother with entinostat, breastfeeding should be discontinued if the mother is treated with entinostat.

3.2.9 HIV-positive patients receiving combination antiretroviral therapy are ineligible because of the potential for pharmacokinetic interactions with entinostat. In addition, these patients are at increased risk of lethal infections when treated with marrow-suppressive therapy. Appropriate studies will be undertaken in patients receiving combination anti-retroviral therapy when indicated.

3.2.10 Serious or non-healing wound, ulcer or bone fracture.

3.2.11 Major surgical procedure, open biopsy, or significant traumatic injury within 28

days prior to day 1 therapy.

[figure not shown]
[figure not shown]
3.2.12 Anticipation of need for major surgical procedures during the course of the study

3.2.13 Left ventricular ejection function <45%.

### 3.3 Inclusion of Women and Minorities

Both men and women of all races and ethnic groups are eligible for this trial.

## 4. TREATMENT PLAN

Treatment will be administered on an inpatient/outpatient basis. Patients will be admitted to the hospital unit with intensive care capabilities for the administration of high dose aldesleukin. Reported adverse events and potential risks are described in Section 5. Appropriate dose modifications for entinostat and aldesleukin are described in Section 5. No investigational or commercial agents or therapies other than those described below may be administered with the intent to treat the patient’s malignancy.

The case report form will capture the concurrent use of all other drugs, over-the-counter medications, or alternative therapies.

#### **4.1 Entinostat / aldesleukin administration and definition of Dose-Limiting Toxicity (DLT)**

Patients with metastatic renal cell carcinoma and no prior therapies will be eligible for treatment. One cycle of treatment (84 days) will consist of 2 courses of high dose aldesleukin 600,000 units/kg administered IV every 8 hrs. on day 1-5 and day 15-19 ( $\pm$  7 days) (maximum 28 doses), and entinostat orally (1-2 hrs. prior to aldesleukin infusion) given every 2 weeks starting on day-14, continuously. Entinostat is to be taken on an empty stomach, at least 1 hour before or 2 hours after a meal. Tumor response assessment will be performed on week 11 ( $\pm$  7 days). In the event of clinical benefit (stable disease or tumor shrinkage) patients will receive a second cycle of therapy.

Entinostat will continue every 2 weeks ( $\pm$  7 days dependent on adjustments necessary for aldesleukin dosing) until documented disease progression or 8 weeks following documented complete response. Patients with evidence of tumor shrinkage may receive up to 3 cycles of high dose aldesleukin therapy. Cycle 2 will start on or within 2 weeks following day 85 (or last day of cycle dependent on dosing adjustment) as in cycle 1. Cycle 3 can start within 2 weeks after completion of cycle 2. Patients with stable disease by RECIST V.1.0 criteria, but without evidence of tumor shrinkage after two cycles will receive only entinostat until disease progression is documented.

In order to assess the effect of entinostat versus the combination on the proposed correlative pharmacodynamic parameters, initial treatment will be with entinostat monotherapy, followed by combination with high dose aldesleukin. The Phase I starting dose level of entinostat will be 3 mg PO every 2 weeks. The first dose level will have a minimum of 3 patients treated unless the first 2 patients experience dose-limiting toxicity(s) (DLT) before 3rd patient is enrolled. DLTs are defined as extended grade 4 toxicity (duration of one week or more) during the first 45 days of treatment. If DLTs occur in 1 patient treated at the starting dose level, a minimum of 3 or 4 patients will be treated at this dose level. If DLT occurs in more than 1 patient in the first 6 patients, patients will be treated at a lower dose level (entinostat 1 mg PO every 2 weeks, dose level 0) and DLT will be evaluated similarly. If DLTs occur in  $\leq$  1/6 patients, dose level 1 will be considered the recommended Phase II dose. If no DLTs occur at the starting dose level 1, 3 or 4 patients will be treated at the next dose level (level 2) with 5 mg PO every 2 weeks (wait 45 days for DLT assessment on first 2 patients before 3rd patient is enrolled). If no DLTs occur at dose level 2, this dose level will be recommended for the phase II portion of the study. If DLTs occur in  $\geq$  1 patient, another 3 patients will be treated at this dose level. If DLT occurs in  $\geq$  2 patients in the first 6 patients, dose level 1 will be the recommended for the Phase II. If DLTs occur in  $\leq$  1/6 patients, dose level 2 will be considered the recommended Phase II dose. Patients who experience extended grade 4 toxicity (duration of one week or more) and recover to  $\leq$  Grade 1 (or to pretreatment baseline level toxicity) may continue treatment at the next entinostat lower level. Once the entinostat has been dose reduced, patients must remain at the reduced dose for the rest of the study. Patients may have their dose de-escalated twice or up to dose level 0 before being removed from the treatment. Patients will be allowed to remain on the therapy provided that they are tolerating the treatment and do not develop progressive disease. No dose de-

escalation for aldesleukin will be performed.

#### Dosing levels

Dose Level	Entinostat (mg, every 2 weeks, PO)	Aldesleukin (IU/kg, every 8hrs, IV)
0	1	600,000
1	3	600,000
2	5	600,000

Patients will receive only entinostat during the “maintenance” (between cycles) period. During Phase II, patients receiving 5 mg entinostat during the “maintenance” period will be given the option to dose escalate entinostat to 10 mg PO if tolerated except two weeks before and two weeks after administration of aldesleukin.

The recommended dose of 5 mg PO every 2 weeks was determined in the Phase I portion of the study. This cohort will be expanded in the phase II portion so that 36 new patients will be treated at this dose level. The evaluations for the phase II component of the study will be identical to the phase I portion.

Compliance will be assessed via patient diaries Also, pill containers will be returned to the study doctor or nurse at the end of each cycle.

#### 4.2 Duration of Therapy

Patients may continue on therapy until one of the following criteria applies:

- Disease progression,
- Unacceptable toxicity.
- Patient decides to withdraw from the study.
- General or specific changes in the patient’s condition that renders the patient unacceptable for further treatment in the judgment of the investigator.
- The study is closed.

#### 4.3 Duration of Follow Up

Follow up safety evaluations will occur 30 days (+/- 4 days) after last dose of study drug or until resolution of any drug related toxicity (telephone contact is acceptable). Follow up will include review of concomitant medications and adverse events.

Patients (both Phase I and Phase II) will be followed up after completion of therapy every three months for survival assessment (telephone contact is acceptable) or until completion of primary endpoint/ termination of study.

### 5. DOSING DELAYS/DOSE MODIFICATIONS

The CTEP Active Version of the NCI Common Terminology Criteria for Adverse Events (CTCAE) [[http://ctep.cancer.gov/protocolDevelopment/electronic\\_applications/ctc.htm](http://ctep.cancer.gov/protocolDevelopment/electronic_applications/ctc.htm)] will be used to classify toxic effects of therapy. Patients with life-threatening or persistent, severe toxic reactions to aldesleukin will receive no further treatment with this agent. Specific toxicities, which require special consideration, are discussed below. Previously unknown or severe toxicities will be reported to the PI as Adverse Drug Reactions.

## 5.1 Entinostat Treatment Modification for Adverse Events

**Patients who experience any Grade 3/4 toxicity related to entinostat during the period off aldesleukin should stop the offending drug up to one dose. If the patients recover to  $\leq$  Grade 1 (or to pretreatment baseline level of toxicity), they may continue treatment with entinostat at the next lower dose.** Once the dose has been reduced, patients must remain at the reduced dose for the remainder of the study. Patients may have their dose reduced down to the lowest dose level 0 (1mg). If the patient misses or vomits a dose of entinostat he/she will skip that dose and notify the research nurse. If a patient has to miss more than one dose of entinostat due to grade 3/4 toxicity during the period off aldesleukin he/she will discontinue entinostat.

## 5.2 Adverse Events with entinostat

Risks to patients receiving entinostat have been minimized with careful monitoring by trained and experienced investigators and evaluation of laboratory safety parameters at appropriate intervals. The following points should be considered for the prevention or minimization of potential adverse events and other risks related to entinostat:

- *Nausea and vomiting:* Antiemetics may be administered to prevent or control nausea or vomiting.
- *Diarrhea:* Antidiarrheal agent(s) may be used in the event of diarrhea.
- *Neutropenia:* The patient should be closely followed for fever, focal signs of infection, and neutrophil nadir. Standard growth factor support may be considered unless excluded in the individual clinical protocols.
- *Anemia:* RBC transfusion support may be given for anemia, particularly when hemoglobin falls below 8 g/dL or as instructed in the individual clinical protocols.
- *Thrombocytopenia:* If bleeding develops or invasive procedures are planned, platelet transfusions may be administered in accordance with standard practice or as instructed in the individual clinical protocol.
- *Hypophosphatemia and other electrolyte abnormalities:* Careful monitoring of electrolytes during treatment with entinostat is recommended and electrolyte supplementation may be warranted. In clinical studies, abnormalities in most patients were successfully managed with supplementation, allowing continued treatment without interruption.

- *Renal abnormalities:* Based on mild increases in creatinine seen in a few patients and results of nonclinical studies, monitoring of renal function is recommended during treatment with entinostat. If clinically significant changes in renal function occur, modification of entinostat dose should be considered.

Entinostat may cause fatigue or malaise; advise patient to exercise caution while driving a vehicle or operating machinery.

Administration of entinostat is contraindicated in patients with a history of allergy to entinostat or other medications that have a benzamide structure (e.g., tiapride, remoxipride, clebopride).

Careful monitoring of patients for signs of infection or reactivation of past infections is recommended, as reactivation of infection has been reported in patients treated with entinostat, in some cases without evidence of neutropenia. The clinical significance of this finding and the potential association with entinostat is unknown.

### 5.3 Aldesleukin Treatment Modification for Adverse Events

Modification of the treatment protocol will occur by withholding doses of aldesleukin rather than continuing therapy at a reduced dose (see Appendix C). Missed doses of aldesleukin will not be made up. Dose of aldesleukin will be withheld for:

- 5.3.1 Hypotension refractory to fluids and pressors or requiring unacceptably high pressor doses
- 5.3.2 Anuria for >24 hours and unresponsive to fluid replacement and low-dose dopamine
- 5.3.3 Respiratory distress requiring oxygen >4 liters to maintain O2 saturation >95%.
- 5.3.4 Confusion (mental status changes can progress to paranoia despite discontinuation of aldesleukin; it is imperative that the aldesleukin be stopped at any sign of persistent confusion or disorientation).
- 5.3.5 Sustained ventricular tachycardia or any sign or symptom of myocardial ischemia or myocarditis. Patients experiencing sustained ventricular tachycardia or myocardial ischemia should not receive further treatment with aldesleukin
- 5.3.6 Metabolic acidosis with HCO3 <18, despite attempts to correct with IV HCO3.
- 5.3.7 Atrial fibrillation or myocarditis.
- 5.3.8 Documented systemic infection.
- 5.3.9 Any other serious toxicity that is not controlled at time of next dose.

## 5.4 Specific aldesleukin Toxicity Management

Several treatment-related toxicities have been uniquely associated with the administration of high-dose aldesleukin. The frequency of Grade 3 and Grade 4 toxicities in Cycle 1 ranges, for example, from 56.8% hypotension to 14.7% neurological, and 13.7% hematological, neurological, pulmonary, renal/electrolytes. Antihypertensive medication should be stopped prior to aldesleukin therapy.

Recommendations for management of the more significant toxicities typically seen with high-dose bolus aldesleukin are as follows (the following are only optional guidelines for toxicity management):

### 5.4.1 Fluid Replacement.

Excessive fluid replacement will increase the patient's likelihood of developing pulmonary edema. It is suggested that when intravenous access has been established; begin administration of normal saline at 75cc/hour IV. Fluid replacement should be given to allow patients to gain approximately 1kg/day. Once patients have gained greater than 5% of baseline weight, additional fluid boluses should not be given to maintain blood pressure. Furosemide should not be given unless symptomatic fluid retention develops and blood pressure is adequate.

### 5.4.2 Hypotension

Administration of high dose aldesleukin leads to decreased peripheral vascular resistance and consequent hypotension. In order to manage this toxicity, the physician may utilize the following guidelines:

1. Monitor patients in a setting capable of providing ICU level care.
2. Prior to starting aldesleukin therapy determine a minimum tolerated blood pressure (MTBP). For patients under age 40 and with no prior history of ischemic or valvular heart disease, the MTBP can be a systolic blood pressure (SBP) of 80 mmHg, while the MTBP for all other patients should be a SBP of 85-90 mmHg based on perceived risk of cardiac toxicity.
3. When a patient's systolic BP falls below the MTBP, suggested therapy may involve (in the following order):
  - a. Begin fluid boluses (250cc normal saline IV over 15 min. may repeat x 2) until SBP is > MTBP.
  - b. Should fluid boluses fail make the SBP > MTBP, phenylephrine should also be instituted (0.1-2 mcg/kg/min) to maintain SBP.
  - c. If blood pressure cannot be maintained on phenylephrine alone, or if unacceptable tachycardia develops, treatment with dopamine (1-6 mcg/kg/min) should be added to sustain blood pressure.

#### 5.4.3 Management of Arrhythmias/Myocarditis.

If significant arrhythmias occur at any stage in the patient's treatment (whether on pressor agents or not), the possibility of myocardial ischemia/infarction must be excluded by both EKG and cardiac enzyme assessment. Patients who develop atrial fibrillation should have aldesleukin doses held. Therapy may resume when the patient converts to normal sinus rhythm and is hemodynamically stable. If a significant supraventricular arrhythmia occurs while a patient is on dopamine therapy; phenylephrine should also be substituted for dopamine as initial blood pressure support. Patients experiencing sustained ventricular tachycardia or documented myocardial ischemic episodes during therapy should not receive further treatment with aldesleukin. Patients with myocarditis may resume treatment in subsequent courses if CPK returns to normal. A cardiac MUGA stress test documenting normal cardiac function should be performed prior to restarting therapy.

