#### 5.4.6 Other Toxicities

Increases in the serum creatinine to 2.0-3.5 mg/dl and total bilirubin to 3.0-10.0 mg/dl are common and reversible upon cessation of treatment. Doses of aldesleukin have not generally been withheld for renal and hepatic dysfunction alone. Although toxicity may become severe, recovery usually occurs following cessation of aldesleukin and vigorous supportive care is warranted.

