### During Therapy Assessment and Interventions

- Start maintenance IV at 100 cc hr before IL-2 is started.

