### DOSE MODIFICATION FOR HDIL-2

(Delay or discontinuation only; no dosage adjustment)

System	Relative Criteria	Absolute Criteria
Cardiac	Sinus Tach 120-130	Sinus Tach >130 (persists after correcting hypotension, fever, stopping dopamine) EKG changes of ischemia Atrial fibrillation Supraventricular tachycardia Ventricular arrhythmias (frequent PVCs, bigeminy, v-tach) Elevated CPK-MB
Dermatologic		Moist desquamation
Gastrointestinal	Diarrhea, 1000 cc/shift  Ileus/abdominal distention	Diarrhea, 1000 cc/shift x 2 Vomiting not responsive to medication Severe abdominal distention affecting breathing Severe abdominal pain, unrelenting
Hemodynamic	Max Neo-Syneprine	Max Neo-Syneprine

NCI Protocol #: 7870

Protocol Version Date 5/29/19

page 71 of 79

	1-1.5 ug/kg/min	1.5-2.0 ug/kg/min
	Min Neo-Syneprine	Min Neo-Syneprine
	>0.5 ug/ kg/ min	> 0.8 ug/ kg/ min
Hemorrhagic	Guaiac+ sputum, emesis, Platelets 30-50,000/mm 	Frank blood in sputum, emesis, stool Platelets <30,000/mm 
Infectious		Strong clinical suspicion or documented
Neurologic	Vivid dreams Emotional lability	Mental status not reversible in 2 hrs. Disorientation Hallucinations
Pulmonary	Resting shortness of breath 3-4 L O 2 NC for sat >95%	>4 L O 2 by NC for sat >95% 40% O 2 mask for sat > 95% Endotracheal Intubation
	Rales 1/3 up chest	Rales 1/2 up chest Pleural effusion requiring tap or chest tube while on therapy
Renal	Urine 80-160 cc/8 hour Urine 10-20 cc/hr Creatinine 2.5-2.9 mg/dl	Urine <80 cc/8 hour Urine <10 cc/ hr Creatinine >3.0 mg/dl
Weight Gain	15% weight gain over baseline	

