## INTERVENTION

### Observation category   Action

≤ 3 Relative criteria	Initiate corrective measures
>3 Relative criteria	Stop IL-2 for current course
1 Absolute criterion	Stop IL-2 for current course

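### Atrial fibrillation on IL-2 is a dose hold with restart in sections 5.3.7 and 5.4.3 but a stop for the course in Appendix C, and no precedence is stated

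*Combined protocol and SAP*

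**What the plan says.** **Atrial fibrillation.** Section 5.3.7 lists it among the reasons for withholding an aldesleukin dose. Section 5.4.3 repeats the hold and adds: "Therapy may resume when the patient converts to normal sinus rhythm and is hemodynamically stable". The same paragraph limits re-treatment after myocarditis to later courses and rules out further aldesleukin after sustained ventricular tachycardia or documented ischemia. Atrial fibrillation has neither limit. In Appendix C, the table of dose modifications puts atrial fibrillation in the absolute column, and the intervention table gives the action for one absolute criterion: "Stop IL-2 for current course".

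**Creatinine.** Section 5.4.6 calls rises to 2.0-3.5 mg/dl common and reversible and says: "Doses of aldesleukin have not generally been withheld for renal and hepatic dysfunction alone". Appendix C has "Creatinine >3.0 mg/dl" as an absolute criterion and 2.5-2.9 mg/dl as a relative one.

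**Urine output.** Section 5.3.2 withholds for "Anuria for >24 hours and unresponsive to fluid replacement and low-dose dopamine". Appendix C makes "Urine <80 cc/8 hour" absolute.

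**Fluids.** Section 5.4.1 suggests: "begin administration of normal saline at 75cc/hour IV". Appendix C says: "Start maintenance IV at 100 cc hr before IL-2 is started".

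**Status of the texts.** Section 5.3 is worded as a rule and refers the reader to Appendix C. Section 5.4 introduces its recommendations as optional. Appendix C is titled as guidelines and says that absolute criteria are generally a reason to stop, but its intervention table is written as instructions. No order of precedence is given.

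**The concern.** A clinician whose patient goes into atrial fibrillation and converts a few hours later can find support in the protocol for restarting IL-2 in the same course and for ending that course. These are different treatments, and the protocol does not choose between them. Missed doses are not made up (section 5.3), so the choice fixes how much IL-2 the patient receives in that course.

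Patient safety comes first, because these passages decide whether a toxic drug continues after a cardiac event. Next is consistency: the trial is multicenter (section 10.5 and Appendix D), so IL-2 exposure could vary by site for reasons unrelated to the patient. Last, section 11.2 plans to summarize the number of IL-2 doses in the first cycle and the toxicity after the scheduled ninth dose. Those summaries are harder to interpret if the stopping rule differed between sites.

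**Working it through.** The protocol states no figure for this point, so the check sets the texts side by side and then counts doses.

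| Sign | Sections 5.3 / 5.4 | Appendix C | Can both be followed? |
|---|---|---|---|
| Atrial fibrillation that converts | Hold, then resume (5.3.7, 5.4.3) | Absolute criterion: course stops | No, if 5.4.3 is read as written |
| Creatinine above 3.0 and up to 3.5 mg/dl | Generally not a reason to withhold when alone (5.4.6) | Absolute criterion | Thresholds differ, but 5.4.6 describes practice and does not instruct |
| Urine below 80 cc/8 h without 24 h of anuria | Not named as a reason (5.3.2) | Absolute criterion | Yes: 5.3.2 does not require dosing to continue until then |
| Starting IV fluid | 75 cc/hour (5.4.1) | 100 cc/hour | No, but neither rate is an IL-2 dosing rule |

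**Which atrial fibrillation events are affected.** Section 5.6.3 ends therapy for grade 4 dysrhythmia, and for grade 2 or 3 dysrhythmia that is not easily controlled. The conflict therefore concerns episodes short of that, which convert and leave the patient stable.

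**Dose count for one atrial fibrillation event.** Inputs: at most 28 doses per cycle in two courses (section 4.1); dosing every 8 hours; missed doses not made up (section 5.3); a delay of more than 24 hours ends the course (Appendix C, IL-2 dosing). Assumption: the 28 doses split evenly, 28 / 2 = 14 per course.

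Let the event follow dose k, and let m doses be held before conversion. At 8-hour intervals the 24-hour limit allows m = 1, 2 or 3.

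- Resume reading: doses in that course = 14 - m.
- Stop reading: doses in that course = k.
- Difference = 14 - m - k.

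Results:

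- k = 5, m = 1: 13 versus 5, a difference of 8.
- m = 1, k from 1 to 12: differences from 12 down to 1.
- m = 3, k from 1 to 10: differences from 10 down to 1.

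If the event comes so late that no scheduled dose remains after the hold, the readings give the same count.

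**Urine output.** 80 cc / 8 h = 10 cc/hour. One 8-hour interval can meet the Appendix C criterion, while section 5.3.2 names more than 24 hours, that is, more than three such intervals. Appendix C also varies internally: its narrative asks for more than 10-20 cc/hour before further dosing, and its corrective-measures table for at least 20-30 cc/hour.

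**Fluids.** 75 x 24 = 1,800 cc, or 1.8 L/day. 100 x 24 = 2,400 cc, or 2.4 L/day.

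**Response rule.** For n = 36 and 11 or more responses, the exact binomial gives P(X >= 11 | p = 0.20) = 0.0889 and P(X >= 11 | p = 0.40) = 0.9096, so the type II error is 1 - 0.9096 = 0.0904. Both match the 0.09 stated in section 11.3. Nothing in the IL-2 dosing text enters this calculation.

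**The case against.** The strongest reply is that most of this text is not binding. Section 5.4 says that its recommendations are optional, and the atrial fibrillation restart, the creatinine sentence and the 75 cc/hour rate all come from there. Appendix C is titled as guidelines and qualifies its absolute criteria. Section 5.3 is open-ended: item 5.3.9 covers any other serious toxicity not controlled by the next dose, and the section points to Appendix C.

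Much of that stands. The creatinine sentence reports how dosing has generally been handled for renal dysfunction alone, and Appendix C says that creatinine is weighed in dosing decisions. For urine output, a site can stop under Appendix C without breaching section 5.3.2. A reader might infer that these two are direct contradictions, or that a site which ignored Appendix C would clearly be compliant. The documents do not support either. They show different thresholds with no stated precedence.

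The reply does not dispose of atrial fibrillation. The dose-level hold is also in section 5.3.7, which is not labelled optional, and the stop for the course is in the appendix to which section 5.3 refers. One could reconcile them by reading section 5.4.3 as resumption in a later course. But it does not say so, and it sets exactly that limit for myocarditis in the same paragraph. If every source is advisory, the protocol has no defined rule for this event.

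**Conclusion.** The point holds, mainly for atrial fibrillation: the hold-and-resume text and the stop-for-the-course text differ for the same event, and nothing says which governs. For creatinine and urine output the defect is the lack of a precedence statement. The fluid rates are a supportive-care inconsistency and should not be counted as an IL-2 hold rule.

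The same event can be managed differently at two sites. The size for one atrial fibrillation event is about 1 to 12 doses in the affected course, assuming 14 doses per course, one to three held doses and at least one scheduled dose left. The documents do not say how often such events occur, so no trial-wide effect can be given.

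Three stronger conclusions may tempt a reader and are not supported:

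- **That all 28 doses of a cycle are at stake.** The Appendix C action ends the current course only, and a cycle has two.
- **That the toxicity stopping boundary in section 11.4 is affected.** It counts extended grade 4 toxicity, defined in sections 4.1 and 11.2 as lasting a week or more. Nothing shows that atrial fibrillation that converts, creatinine of 3.0-3.5 mg/dl or one interval of low urine output would become such an event.
- **That the primary analysis is weakened.** The 11-of-36 rule and its error rates are unchanged.

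The IL-2 dose summary is a Phase I secondary objective. Section 4.1 says that Phase II evaluations match Phase I, but section 11.3 names no dose-count analysis for Phase II.

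**What to change.** The clinical team should reconcile sections 5.3 and 5.4 with Appendix C so that each sign has one hold, resume or stop rule. If they prefer to keep the texts separate, one sentence in section 5.3 should state which source governs when they differ, and which parts are binding and which advisory. For atrial fibrillation, the text should say explicitly whether resumption means the same course or a later one, and how this fits with section 5.6.3. The urine-output figures within Appendix C and the two starting fluid rates can be aligned in the same edit. Which rule or threshold to adopt is a clinical decision, and this review takes no position on it.

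The cost is an amendment to wording, with investigator review and the usual CTEP and IRB approval (section 10.1). It needs no added procedures, visits or patients, and no change to the sample size or decision rules.
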